9.3 Recruitment rates

A total of 350 participants will be recruited across approximately 5 sites over a period of 3 to 6 months. Sites may be asked to pause randomisation across certain sub-cohorts to allow for a broad representation of disease types.

9.4 Informed consent

A full explanation should be given to the patients including the aims of the trial, what this will involve for the participant and possible adverse effects. This conversation should be structured around the Participant Information Sheet (PIS) and may be undertaken remotely. The patient information sheet may be sent to them in advance electronically or through the post prior to the meeting. The individual should be given adequate time (ideally 24 hours) to read the PIS, consider the trial and the opportunity to ask questions, before being asked to sign the Informed Consent Form (ICF). Consent may be taken by the local PI or a trained member of the trial team delegated to do so on the delegation log.

Informed consent will be obtained in writing by completing the consent form by both parties. One copy of the signed Consent Form to be given to the participant, and the original copy to be kept in the investigator site file and a further copy to be kept with the participant's hospital notes. Only when written informed consent has been obtained from the participant and they have been enrolled into

the trial can they be considered a trial participant. No trial procedures should be conducted prior to consent. Details of all patients approached about the trial should be recorded electronically on the Patient Screening/Enrolment Log (see section 9.2).

The right of the participant to refuse to participate in the trial without giving reasons must be respected. However, the reason for doing so should be recorded and the participant will remain within the trial for the purpose of follow up and data analysis according to the treatment option to which he/she has been allocated. Similarly, the participant must remain free to withdraw at any time from the protocol treatment without giving reasons and without prejudicing his/her further treatment.

New safety information may necessitate changes to the PIS and ICF. In this event, it may be necessary to ask some, or all, participants to decide whether to re-consent or withdraw from the trial. Decisions on whether, and which, participants need to re-consent will be made by sponsor / TMG and the decision will be documented in the TMF. Timelines for the re-consent process to be completed will be set. The CTR will communicate local requirements to participating sites and initiate a process to track progress.

The participant's GP should be informed of their involvement in the trial. A template GP letter is provided electronically.

Trial and clinical data and samples will be shared with AstraZeneca and the wider trial team as part of the trial and may also be shared outside of the trial team for research purposes by national and international organisations. The data will be de-identified so that the participants cannot be identified outside of Cardiff University, AstraZeneca and the Sponsor through reasonable measures. Participants consenting to the trial will be consenting to future use of their de-identified data and samples in research outside of the trial under public interest. All research proposals will be reviewed by the CTR and Sponsor to ensure for scientific integrity and data and sample safeguarding.

Participants may also be asked to consent to NHS Information Centre Flagging (and Scottish and Northern Irish equivalents) so that the date and cause of death may be collected if not available. This will be optional and additional to the standard informed consent.

Participant consent is requested to collect NHS Numbers to utilise NHS data for future research, through Cancer Research UK and the National Cancer Intelligence Network (NCIN).

Participants will also be asked whether they are happy to be contacted about further information on the trial or other related studies. Information about the trial will be made available on the trial website.

9.5 Registration and randomisation

Once participants are identified, consented and deemed eligible, they will be assigned a unique trial ID and randomised by the treating team via the same portal. Participants will be randomised to receive one of two boosters in a 1:1 ratio:

Arm 1: Comirnaty bivalent (Original/Omicron BA.1)

Arm 2: Spikevax bivalent (Original/Omicron)

The trial will be unblinded and therefore both the participant and the site research team will know the treatment allocation. The trial pharmacist, research nurse and laboratory team will be notified of the randomisation allocation and trial ID number. A copy of the Randomisation Confirmation, signed Informed Consent Form, and Eligibility Checklist should be filed within the Investigator Site File.

Registration and Randomisation

Patient enrolment for this trial will be through the use of a web-based system: https://trials.cardiff.ac.uk/portal

Details of how to access the system will be supplied to Investigators as part of the trial set-up.

If any problem with the web-based system or it is unavailable, please email the trial team:

[contact]

10 Withdrawal & lost to follow-up

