4.7.1 Hypotheses to be tested

1) That treatment with AZD7442 in combination with a SARS-CoV-2 vaccine is safe and well tolerated,

2) That vaccination with a SARS-CoV-2 vaccine does not reduce AZD7442 titres in humans and

3) That AZD7442 in combination with a SARS-CoV-2 vaccine enhances immune responses to SARS-CoV-2.

5 Trial objectives/endpoints and outcome measures

We propose to test the following objectives:

Table 1: Objectives and outcome measures

	Objectives	Outcome measures
Co-Primary	To assess the pharmacokinetics of AZD7442 administered as a single dose of 600 mg IM in immunosuppressed patients	Serum samples will be taken at Day 0 (Predose AZD7442), and days 28, 112 and 180 post AZD7442 treatment and samples shipped to an AstraZeneca approved laboratory for Pharmacokinetics (PK) analysis.
		Samples collected for analyses of AZD7442 serum concentration may also be used to evaluate safety or efficacy aspects related to concerns arising during or after the trial. PK results from the trial will be compared to results from other phase III studies with AZD7442 such as PROVENT.
	To assess the safety and tolerability of a single IM dose of AZD7442, followed by SARS-CoV2 vaccine booster 28 days later with reference to serious adverse events (SAEs) in highly vulnerable patients.	SAE reporting throughout the trial using CTCAE V5.0
	To assess the SARS-CoV-2 specific humoral and cellular immune response against SARS-CoV-2 variants, when a SARS-CoV-2 vaccine is administered 28 days after AZD7442 in patients who are immune suppressed.	The function and magnitude of SARS-CoV-2 specific antibody and T cell responses will be measured at baseline and at additional multiple timepoints after the administration of AZD7442.
		Assays will quantify the amount of serum antibodies to the spike (S) and the nucleocapsid (N) antigens of SARS-CoV-2. This assay will enable the discrimination of antibody responses to SARS-CoV-2 that results from vaccination and/or SARS-CoV- 2 infection. Ab function, including viral neutralisation will be assessed.

		The magnitude and function of SARS-CoV-2 specific T cell responses following the booster vaccination will use assays that give insight into T cell function. Laboratories will measure neutralizing antibodies to SARS-CoV-2 using validated wild-type neutralization assay or pseudo- neutralization assays.

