	To assess the effect of a SARS-CoV-2 vaccine on AZD744 monoclonal antibody titres.	Serum samples will be taken at Day 0 (Predose AZD7442), and days 28, 56, 112 and 180 post AZD7442 treatment and vaccination and samples shipped to an AstraZeneca approved laboratory for quantification of the AZD744 monoclonal Abs generated by therapeutic vaccination, natural infection and vaccinations.
Secondary	The incidence of participants who have a post-treatment response (negative/low at baseline to positive at any time post-baseline) for SARS-CoV-2 nucleocapsid antibodies.	Measurement of SARS-CoV-2 anti NP Abs assessed over the course of the study.
	The incidence of SARS-CoV-2 infection in trial participants.	Self-reported throughout the study duration and assessed at follow up visits.
		Lateral flow testing for SARS-CoV-2 infection in a subset of asymptomatic participants on days 0, 28, 56, 112 and 180. If the lateral flow test is positive for SARS-CoV-2, a nasal PCR swab will be taken to be sent for PCR testing.
		Ad-hoc PCR testing in all symptomatic patients.
		Measurement of SARS-CoV-2 Anti-NP IgG titres
	Sequencing of confirmed SARS-CoV-2 infections to identify SARS-CoV-2 variant and potential AZD7442 escape variants.	Lateral flow testing for SARS-CoV-2 infection in a subset of asymptomatic participants on days 0, 28, 56, 112 and 180. If the lateral flow test is positive for SARS- CoV-2, a nasal PCR swab will be taken to be sent for PCR testing.
		Ad-hoc PCR testing in all symptomatic patients.

	To assess the behaviour of the trial participants before and after trial treatment.	Validated behavioural questionnaire completed by the participants at baseline and at multiple time points over the course of the trial.
	To assess if different SARS-CoV-2 vaccines will preferentially enhance humoral and/or T cell responses in immune suppressed patients receiving AZD7442	Assessment of SARS-CoV-2 humoral and cellular responses in patients randomised to receive different SARS-CoV-2 vaccines
	To assess the severity of SARS-CoV-2 infection contracting COVID-19 within the duration of the trial.	Assessment of SARS-CoV-2 severity in participants contracting COVID-19 within the duration of the trial using the WHO Clinical Progression Scale.
Exploratory	To investigate the mechanism of immunogenicity across disorder/disease treatment across the cohorts.	Immune data will be evaluated within and between disease and treatment cohorts.

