12.1 Analysis

Immunogenicity will be assessed by a variety of immunological assays at University of Oxford research laboratories or at designated specialist laboratories. This will include:

- Quantify antibody responses to SARS-CoV-2 Spike and non-Spike antigens
- Assessment of T-cell responses using ex vivo ELISpot assays for interferon gamma and flow cytometry assays or other relevant assays of cellular function and phenotype.
- Assessment of neutralising antibody against live and/or pseudotype SARS-CoV-2 virus variants
- B cell analyses, and Peripheral blood mononuclear cell (PBMC) analysis.

Serology and PK analysis will be conducted at research laboratories as specified in the Laboratory Manual according to laboratories SOPs.

A subset of participants will be regularly tested for SARS-CoV-2 infection. All samples positive for SARS-CoV2 infection will be sequenced to identify escape variants.

DNA analysis of genetic polymorphisms potentially relevant to vaccine immunogenicity and/or SARS-CoV-2 pathogenesis or SARS-CoV-2 therapeutics and gene expression studies amongst others may be performed at the discretion of the Investigators.

This is not an all-inclusive list: additional assays will be performed as more information becomes available about the immune response elicited during the trial.

Should a participant have a SARS-CoV-2 infection, severity should be assessed using the WHO Clinical Progression Scale (see Appendix 2).

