15.2 Blinding

This is an open label trial.

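### Section 9.5 discloses the booster allocation to an undefined laboratory team, with no exception for staff who run or read the assays behind the randomised vaccine comparison

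*Protocol*

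**What the plan says.** Section 9.5 first draws a limited consequence from the open-label design: "The trial will be unblinded and therefore both the participant and the site research team will know the treatment allocation". The next sentence widens the circle: "The trial pharmacist, research nurse and laboratory team will be notified of the randomisation allocation and trial ID number". The trial ID and the arm therefore go out together.

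Section 15.2 reads in full: "This is an open label trial". It says nothing about masking the people who measure the outcome.

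Section 12.1 says who measures immunogenicity: "Immunogenicity will be assessed by a variety of immunological assays at University of Oxford research laboratories or at designated specialist laboratories". The list of methods includes this item: "Assessment of T-cell responses using ex vivo ELISpot assays for interferon gamma and flow cytometry assays or other relevant assays of cellular function and phenotype". It also covers antibody quantification and neutralisation, and says that further assays will be added as knowledge of the immune response grows.

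Table 1 in section 5 makes these readouts co-primary: "The function and magnitude of SARS-CoV-2 specific antibody and T cell responses will be measured at baseline and at additional multiple timepoints". The same table uses them for the secondary objective on vaccine type, with this outcome: "Assessment of SARS-CoV-2 humoral and cellular responses in patients randomised to receive different SARS-CoV-2 vaccines". Section 16.1.2 analyses the vaccine contrast by ANCOVA with the baseline value as covariate.

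**The concern.** In an open-label trial the participant and the clinic staff know which booster is given. The pharmacist and the nurse need the allocation to supply and give it. The person reading an assay does not obviously need it, so the outcome can still be assessed masked even though dosing is open. Section 9.5 gives that up by an express instruction, so this is not a detail left to a later document.

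The comparison exposed is the booster contrast, the only one in the trial that rests on randomisation. Its outcome is produced in the laboratory. If a reader knows the arm, that knowledge can enter spot counts, gating, the choice to repeat or accept a result, and the choice to exclude a sample. A systematic difference introduced there acts directly on the arm contrast and cannot be separated from a vaccine effect afterwards. Automated serology is less open to this than ELISpot or flow cytometry.

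**Working it through.** This is mainly a question of reading sections together.

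**1. Is the laboratory told the arm?** Yes, by the wording of 9.5. The laboratory team is named alongside the pharmacist and the nurse, and apart from the site research team of the preceding sentence.

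**2. Is masking restored elsewhere?** No. Section 15.2 gives only the open-label label. Sections 12 and 12.1 describe collection, shipping and assays without mentioning allocation.

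**3. Is there a stated need for the laboratory to know?** None was found. Sampling days are the same in both arms (days 0, 28, 56, 112 and 180; section 12 and Table 6). Samples are frozen on site and sent in batches. Trial ID and visit are enough to track them.

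**4. Which comparisons are exposed?**
- Booster A against booster B at day 56 (16.1.2; secondary objective in Table 1): exposed, because the arm is what the reader would know.
- Each cohort against its own baseline or against PROVENT (16.1.1 and the first part of 16.1.2): little affected, because knowing which of two boosters was given does not favour trial patients over controls.
- Day 0 and day 28 samples are drawn before the booster (11.1, 13.1), so the arm cannot have changed the sample itself. Their reading could still be influenced if the arm is already known. Section 13.1 lists randomisation among the baseline assessments, whereas 15.1 places it at day 28, so the timing of disclosure is itself unclear.

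**5. Does the protocol give a figure to work from?** Section 15.3 gives 70 per group for a difference of 0.5 log with SD 1, 90% power and 5% significance.
- One-sided: n = 2(1.645 + 1.282)² / 0.5² = 68.5, so 69 per group, or 70 by the t-test version (69.2). The stated 70 is reproduced.
- With 20% loss: 4 × 70 = 280, and 280 / 0.8 = 350. The stated 350 is reproduced.

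Both figures concern IgG against PROVENT volunteers. No figure is given for the booster contrast, and no SD for ELISpot, flow cytometry or neutralisation.

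**6. Sensitivity, on assumed inputs only.** Take SD 1 log, a two-sided 5% test, no covariate adjustment, and an assumed systematic reading shift b between arms. The standard error is √(2/n) with n per arm. The false-positive rate is Φ(−1.96 + b/SE) + Φ(−1.96 − b/SE).

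| n per arm (assumed) | SE | b = 0.05 | b = 0.10 | b = 0.20 |
|---|---|---|---|---|
| 140 (280 split 1:1) | 0.120 | 7.0% | 13.3% | 38.7% |
| 60 (120 split 1:1) | 0.183 | 5.9% | 8.5% | 19.5% |

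The second row assumes that the judgement-based assays are confined to the up to 120 Oxford participants who give additional translational bloods (section 6). The protocol does not say that they are. The values of b come from no document. The table shows how the mechanism works and does not estimate its effect.

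**The case against.** The strongest reply is that the laboratory team may not be the assay laboratories at all. It is listed with the site pharmacist and nurse, in a paragraph that ends with filing in the Investigator Site File. Section 12 has samples processed and frozen on site before they go to the laboratories of section 12.1. The Laboratory Manual, which is not at hand, may send samples out under coded labels. This stands as a limit: it is not established that any assay reader actually knew the arm. It does not remove the point, because 9.5 makes no exception for assay staff and the protocol nowhere says they are masked.

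A reader might infer that the co-primary results are compromised, since the same assays produce them. The documents do not support that. The co-primary immune comparisons are with baseline and with PROVENT, and the vaccine contrast is a secondary objective for which the trial was not sized.

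A reader might also take the larger error rates in the table as the expected damage. They rest on invented shifts and on an IgG SD applied to assays for which the protocol gives none. They also require a consistent lean towards one of two bivalent mRNA vaccines. Both vaccines come from manufacturers other than the funder, and the protocol shows no evident motive for such a lean.

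Finally, it is fair to say that the remedy comes late. Recruitment was paused at the beginning of April 2023 (13.1.1), before version 5.0 was issued. Allocations already sent cannot be recalled.

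**Conclusion.** The point holds as an avoidable weakness in how the randomised between-vaccine comparison is assessed. Section 9.5 instructs disclosure of the arm to an undefined laboratory team, nothing restores masking for assay readers, and no need for them to know is stated. The consequence is a potential bias, chiefly in operator-dependent cellular readouts and confined in practice to a secondary objective. Its size cannot be derived from the document, and the sample size does not change.

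The conclusion rests on reading laboratory team as at least not excluding assay staff. If the sponsor can show that only on-site sample handlers were meant and that assay laboratories received coded samples, what remains is a clarification of wording.

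**What to change.** - **Section 9.5:** remove the laboratory team from those notified of the allocation, or limit it to named site roles that need it. State that assay laboratories receive samples identified by trial ID and visit only.
- **Section 15.2:** keep the open-label statement and add that immunogenicity assays, including decisions to repeat or exclude, are run and read masked to booster allocation until the assay data are locked.
- **Assays already run or allocations already disclosed:** record which laboratories and batches are affected, and mask the remaining batches where possible. Report this alongside the vaccine comparison.

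The cost is a wording change plus some administrative work to trace past disclosures and to arrange masked repeat and exclusion decisions. No visit, treatment or sample size changes. Masking cannot be restored where the reader already knows the arm.

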10.1 Withdrawal

Participants have the right to withdraw consent for participation in any aspect of the trial at any time. The participants care will not be affected at any time by declining to participate or withdrawing from the trial. In addition, a participant may be withdrawn by the investigator or the Sponsor if enrolment into the trial is inappropriate, the trial plan is violated, or for administrative and/or other safety reasons.

A participant may withdraw or be withdrawn from trial treatment for the following reasons:

- Intolerance to trial medication
- Withdrawal of consent for treatment by the participant
- Any alteration in the participants condition which justifies the discontinuation of the treatment in the Investigator's opinion
- Non-compliance

If a participant initially consents but subsequently withdraws from the trial, clear distinction must be made as to what aspect of the trial the participant is withdrawing from. These aspects could be:

- Withdrawal from AZD7442 or booster or both
- Withdrawal from further trial assessments

Data and samples collected from trial visits that have taken place up until the withdrawal date can still be sent but participant will not attend any further visits.

- Withdrawal from future research using excess participant samples Participants will have the option to destroy or keep samples collected prior to withdrawal date
- Withdrawal from future research using data Participants have the option to remove their consent to sharing of their de-identified data outside of the trial for future research.
- Withdrawal from any previous data to be used
 A participant can withdraw consent and request that their trial data is not used in the analysis
 of the trial. Since the legal basis for the processing of trial data is for scientific research
 purposes, which are in the public interest, and is subject to the necessary safeguards, any
 request for deletion of previous data collected will be reviewed by the trial TMG, who will
 consider whether the data should be processed or deleted. Previous reports and publications
 that use the participant's data will not be amended or deleted.
- Withdrawal from any previous sample to be used Participants may request that all previously collected samples are destroyed to prevent use in future research, though it may not be possible to retrieve samples already donated for future research e.g. If samples have been anonymised. Upon notification of a participant withdrawal via the relevant CRF form in the database, samples should be destroyed by the laboratory and noted on the destruction log.

Furthermore, it is important to collect safety data ongoing at the time of withdrawal, especially if the participant withdraws because of a safety event. There is specific guidance on this contained in the Participant Information Sheet but briefly: If a participant wishes to stop taking part in the trial completely, they may need to be seen one last time for an assessment

If a participant wishes to stop taking part in the trial completely, they will need to be seen one last time for assessments and tests.

For participants who consent and subsequently withdraw their consent, the Withdrawal of Consent Form should be completed by the participant and signed by both the participant and the PI or a member of the trial team who has been delegated by the PI to undertake this activity. One copy of the Withdrawal of Consent Form will be given to the participant, the original copy will be kept in the ISF, and a further copy will be kept with the participant's hospital notes.

RDIF

Completed participant withdrawal forms should not be sent to the CTR, since they will contain participant identifiable information. The participating site should advise the CTR of this withdrawal by completing the relevant Withdrawal form on the database.

Any queries relating to potential withdrawal of a participant should be forwarded to RAPID-[contact]

